8.0 Subject Disposition

The number and proportion of subjects in Groups A & B eligible for and compliant with all follow-up examinations will be presented. Subjects who withdraw from the study will be tabulated with the reasons for the withdrawal. Subjects who initiate the procedure, regardless of tolerability outcome or anesthesia effectiveness, will be encouraged to return for all follow-up assessments.

Subject disposition will be summarized for each Group with counts and percentages. Categories summarized will include the number of subjects who signed informed consent, number of screen failures (with reasons), and the number enrolled, completed, and discontinued, as well as reasons for discontinuation. The summary of disposition

will also include the number and percentage of subjects included in each analysis set described in **Section 7**.

9.0 Demographic Characteristics and Medical History

Demographic characteristics including age, sex and race/ethnicity will be descriptively summarized for all enrolled subjects in each of the defined study Groups. Significant medical history will also be summarized for all enrolled subjects in each of the defined study Groups. Demographic characteristics and medical history will be presented separately for each of the Analysis Sets defined for each Group, and by sex.

10.0 Procedure Characteristics and Device Malfunctions

Procedure and device performance characteristics will be summarized using descriptive statistics for each Group, and by treatment for Group A only.

11.0 Co-Primary Endpoint Analyses

11.1 Anesthesia Effectiveness (Group A)

This study will consist of two independent Groups, Group A and Group B. Each Group has its own primary endpoint, each of which must pass the statistical test for the overall study to be considered successful.

Group A subjects will be randomized to either active lidocaine iontophoresis treatment or sham lidocaine iontophoresis treatment. Each subject will each have a VAS score.

The null and alternative hypotheses are:

$$H_0 : \mu_T - \mu_S = 0$$

vs.

$$H_1 : \mu_T - \mu_S < 0$$

where μ_T and μ_S are the mean scores in the treatment and sham arms respectively.

The primary endpoint will be evaluated in the mITT set using a permutation test at a 2.5% significance level. The primary endpoint will be demonstrated if the p-value from the permutation test is less than or equal to 0.025. These analyses will be repeated in the Per Protocol Set.

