Sample Size and Power	
Group A:
 
A sample size of 40 subjects will provide greater than 95% power at the one-sided 2.5% significance level for a permutation test on the difference in mean VAS scores between the two arms. The null and alternative hypotheses are:
 $H_0: \mu_T - \mu_S = 0$ $H_1: \mu_T - \mu_S < 0$ 
Group B:
 
A sample size of 30 subjects will provide greater than 95% power at the one-sided 2.5% significance level for a bootstrap test of the mean VAS score against a performance goal of 4.5. The null and alternative hypotheses are:
 $H_0: \mu \geq 4.5$ $H_1: \mu < 4.5$
------------------------------	------------------------------------------------------------------------------------------------------------------------------------------------------------------------------------------------------------------------------------------------------------------------------------------------------------------------------------------------------------------------------------------------------------------------------------------------------------------------------------------------------------------------------------------------------------------------------------------------------------

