12.2.8. Tolerability (VAS)

The Visual Analogue Scale (Figure 9) is an instrument for assessing procedural pain consisting of a 10cm line, where the ends of the line represent the extreme limits of pain intensity (“No pain” to “Worst possible pain”).⁴² The subject reports their pain intensity by making a mark along the line and the line is measured to convert the subject response to numeric score (0-10 in centimeters). The VAS is validated for use in subjects 8 years of age and older.³⁵ A standardized script will be read to the subject to ensure consistent interpretation of the pain rating task. [REDACTED]

[REDACTED]

[figure not shown]

Figure 9. Visual Analogue Scale (not shown to scale)

[REDACTED]

[REDACTED]

[REDACTED]

[REDACTED]

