12.5.2. Otoscopic Examination and Ear Preparation

An otoscopic exam will be conducted using a microscope for all ears planned for treatment for subjects in Groups A and B prior to procedure. The otoscopic examination will be used to visually examine the condition of the external ear canal and TM. Routine ear cleaning may be conducted, if needed, only to the extent necessary to ensure the tympanic membrane and ear canal are free from matter that may interfere with or influence the evaluation and to ensure visualization of the tympanic membrane. Changes in concomitant medications will be recorded.

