12.5.5. Earset Placement and Drug Instillation

Baseline tolerability will be assessed before placement of the Earset. The Earset ear plug of the size determined in the ear sizing procedure is then placed into the ear canal. Once the ear plug is positioned, the protective liner is removed, exposing the PSA to the ear canal. Circumferential pressure is applied through the ear plug against the surface of the ear canal, ensuring adhesion of the PSA. The Earset's integrated fill system is used to instill the selected drug into the ear canal. This process is repeated for the second ear, as applicable.

The Electrode Cable is snapped to the Return Electrode Patch. The Return Electrode Patch is then attached to the patient at a clean, dry site (such as the shoulder near the base of the neck) that is clear of lesions, bony protuberances and excessive hair. Prior to placing the return electrode on the patient, the investigator will assess the location for pre-existing erythema using the five point Draize erythema score where 0 indicates no erythema, 1 = very slight erythema (barely perceptible), 2 = well-defined erythema, 3= moderate to severe erythema, 4= severe erythema to slight eschar formation.⁴³ The location will be assessed again following iontophoresis.

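### Group A records a baseline tolerability score before treatment, but the visible primary test compares raw post-tap means; adjusting for it is a cheap efficiency gain, not a repair of an invalid test.

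*SAP*

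**What the plan says.** Protocol 12.5.5 requires a pre-treatment assessment: "Baseline tolerability will be assessed before placement of the Earset". The next sentence there, "The Earset ear plug of the size determined in the ear sizing procedure is then placed into the ear canal", puts ear sizing (12.5.3) ahead of placement. Ear cleaning is described earlier still and is optional: "Routine ear cleaning may be conducted, if needed" (12.5.2). Section 12.5.5 is not limited to Group B, and Protocol 11.5 refers to it for Group A blinding. Section 12.2.8 is headed as the tolerability section and describes the VAS, which "is an instrument for assessing procedural pain consisting of a 10cm line".

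The primary outcome is one post-tap score per subject: "Each subject will each have a VAS score" (SAP 11.1). On the test, the same section states: "The primary endpoint will be evaluated in the mITT set using a permutation test at a 2.5% significance level". The protocol summary specifies a "permutation test on the difference in mean VAS scores between the two arms", one-sided at 2.5%. No visible text adjusts for the baseline score, uses change from baseline, or gives that score any other role. Table 2, the Group A schedule, has no row for it. SAP 6.0 stratifies randomization by site; the visible text does not say whether the permutation respects the strata.

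**The concern.** The baseline score is taken before any current or drug, so treatment cannot affect it. If it predicts the post-tap score, leaving it out keeps explainable variation in the error term: differences in how subjects use the scale, and any discomfort left from ear handling. With 20 subjects per arm, that costs some power.

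Both groups must pass for the study to succeed, so a miss in Group A is a miss for the study. SAP 13.1 gives uncertainty about the effect size as the reason for planning 40 subjects rather than 24. Covariate adjustment helps against the same uncertainty without more subjects. It has to be prespecified, because an adjusted test chosen after unblinding would not be credible.

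**Working it through.** **Inputs from the documents.** One-sided alpha 0.025; 1:1 allocation; 40 evaluable subjects (20 per arm); power above 95% with 24 evaluable subjects (12 per arm), from SAP 13.1.

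**Not available.** The assumed difference and SD are blacked out, so the stated power cannot be reproduced. No baseline-outcome correlation r is given; r is an assumption throughout.

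**Step 1: effect implied by SAP 13.1.** For exactly 95% power at 12 per arm, the normal approximation gives d = (1.960 + 1.645) × √(2/12) = 1.472 SD. The noncentral-t solution is 1.541 SD. Since the SAP claims more than 95%, both are lower bounds on the planning effect, about 1.5 SD.

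**Step 2: unadjusted power at 40.** The noncentrality is d × √(20/2). For d = 1.472 it is 4.654, and power on 38 df is 99.5%. For d = 1.541, power is 99.7%.

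**Step 3: what adjustment does to the variance.** With one covariate, the factor is (1 − r²) × (1 + 1/36), where 36 = 40 − 4.
- r = 0: 1.028, a 2.8% penalty.
- r = 0.3: 0.91 × 1.028 = 0.935.
- r = 0.4: 0.84 × 1.028 = 0.863.
- Break-even: 1 − r² = 36/37, so r = √(1/37) = 0.16.

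**Step 4: power with adjustment.** Divide the noncentrality by the square root of the factor and use 37 df.

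| True effect | Unadjusted | r = 0 | r = 0.3 | r = 0.4 |
|---|---|---|---|---|
| 1.472 SD (implied) | 99.5% | 99.4% | 99.7% | 99.8% |
| 0.736 SD (half) | 62.1% | 60.8% | 64.9% | 68.4% |

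At the implied effect the gain is 0.2 to 0.3 points. At half the effect it is 64.9 − 62.1 = 2.8 points and 68.4 − 62.1 = 6.3 points. With an uninformative baseline it is 60.8 − 62.1 = −1.3 points.

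**Step 5: check by simulation.** I simulated normal outcomes with two sites of 20 (10 per arm each, an assumption). Post-tap scores were regressed on baseline without a treatment term, and arm labels were permuted within site (6,000 trials, 1,999 permutations). Under the null, rejection was 2.2% to 2.5% for both the raw and the adjusted test. At half the effect, raw against adjusted power was 61.6% against 64.4% (r = 0.3) and 60.9% against 67.1% (r = 0.4). With an uninformative baseline heaped at its floor it was 61.2% against 60.0%. This agrees with Step 4.

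**The case against.** The strongest reply is that nothing is broken. Under randomization the raw permutation test controls its error rate and the mean difference is unbiased; chance baseline imbalance is already in the reference distribution. That stands. A reader might infer that imbalance passes straight into the estimate as bias. It does not: it is ordinary sampling error, and it matters only as far as baseline predicts outcome.

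The covariate is also less certain than it looks. Protocol 12.5.5 names no instrument; the VAS is inferred from the 12.2.8 heading. The abbreviation list includes a second pain scale, FPS-R, and the text between 12.2.8 and 12.2.10 is blacked out. The order after cleaning and sizing follows section order. Nor is it the same outcome measured earlier, as one might assume: no visible text describes a tap before treatment, so the baseline is at most resting ear discomfort. In healthy volunteers with ear disease excluded, scores near 0 are plausible, and r may be small. This also stands, and it is why the fix names the instrument and carries a fallback.

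Finally, the step from 24 to 40 subjects already addresses uncertainty about the effect, and blacked-out text may hold a supportive adjusted analysis. Both points limit the concern. They leave the visible primary test without a covariate that the protocol has sites collect.

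**Conclusion.** This holds as a minor efficiency point. A pre-treatment score is to be collected, and the visible primary analysis does not use it. At the effect implied by SAP 13.1, the gain from adjustment is under 0.5 points on power already above 99%. If the true effect is about half that, the gain is roughly 3 to 6 points at r of 0.3 to 0.4, and nil or a loss of about 1 point if baseline sits at the floor.

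These sizes rest on the back-solved effect, the assumed r, and 12.5.5 meaning the VAS and applying to Group A. The documents do not support a reading that Group A is underpowered: a case built on, say, 0.9 SD conflicts with SAP 13.1, because 0.9 SD gives only 56% power at 12 per arm (noncentral t), not above 95%. The mismatch between 12.5.5 and Table 2 needs correcting whatever is decided about adjustment.

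**What to change.** Before unblinding:

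1. In SAP 11.1, define the permutation statistic as the arm difference in mean residuals from a regression of post-tap VAS on baseline VAS, fitted without treatment. Permute labels within site, as randomized.
2. Keep the unadjusted permutation test as supportive, and as the fallback if baseline scores show no variation. That rule uses pooled baseline values only, so it does not disturb the error rate.
3. State how a missing baseline score is handled, so that no subject drops out of the mITT set because of it.
4. Name the VAS as the instrument in Protocol 12.5.5 and add the baseline score to Table 2.

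The cost is a few lines of SAP text and code and one schedule row. The downside is a variance penalty of up to about 3% (1/36 = 2.8%) if baseline proves uninformative.

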11.2 Tube Placement Tolerability (Group B)

The Group B primary endpoint is Tube Placement Tolerability defined as mean subject-reported pain score following TDS tube placement using the VAS. The mean pain score for subjects in the Group B cohort, for whom tube placement was attempted, will be evaluated against a Performance Goal pain score of 4.5.

Group B subjects will each have a VAS score that captures the pain associated with tube insertion.

The null and alternative hypotheses are:

$$H_0: \mu \geq 4.5$$

$$H_1: \mu < 4.5$$

where μ is the mean VAS score across subjects.

The primary endpoint will be evaluated in the Per Protocol set using the bootstrap method at a 2.5% significance level. The primary endpoint will be demonstrated if the upper confidence bound of a 95% non-parametric bootstrap confidence interval on the mean score is below 4.5. For bilateral subjects the highest score ('worst ear') will be used as the subject score. If a subject is intended for unilateral treatment, then the score from only the treated ear is collected and included in the analysis. Only completers, i.e., subjects with VAS scores after successful tube insertion in all indicated ears will be included in the primary analysis.

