Prior TULA in office tube delivery study results indicate that tolerability scores are anticipated to be in the mild range. Therefore, it is reasonable to set a performance goal to be superior to (less painful than) moderate pain. Using the VAS, Tusker will demonstrate superiority to a score of 4.5cm (or 45mm), based on Jensen's determined cut point of 45mm for adult VAS scores, showing that the pain associated with in-office tube insertion in adult subjects is mild.

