13.2 Group B Primary Endpoint – Tube Placement Tolerability

[REDACTED]

[REDACTED]

A sample size of 30 evaluable subjects in Group B will provide greater than 95% power at the one-sided 2.5% significance level for a non-parametric bootstrap test of the mean VAS score against a performance goal of 4.5.

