21.0 Multiplicity Adjustment

Groups A & B each have a single primary endpoint tested at a significance level of 2.5%. Each primary endpoint must pass the statistical test for the study to be considered successful. The familywise error rate is therefore controlled at 2.5% and no multiplicity adjustments are planned.

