24.0 Other General Considerations

Raw data will be presented with the exact precision that it was collected on the eCRF or other external data sources.

Percentages will be reported with exactly one decimal place. The mean and standard deviation as well as any corresponding confidence intervals will be reported with one decimal place. Blank fields on an eCRF will be displayed as blank fields in corresponding listings.

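### Does the approximate level of the Group B bootstrap rule, or one-decimal reporting of its bound, undermine the plan's 2.5% error claim?

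*SAP*

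**What the plan says.** Group B is tested against a performance goal of 4.5 on the 0-10 VAS "using the bootstrap method at a 2.5% significance level" (SAP 11.2). The endpoint is met if "the upper confidence bound of a 95% non-parametric bootstrap confidence interval on the mean score is below 4.5". SAP 13.2 plans 30 evaluable subjects and states "greater than 95% power at the one-sided 2.5% significance level for a non-parametric bootstrap test of the mean VAS score".

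For Group A, SAP 11.1 says: "The primary endpoint will be evaluated in the mITT set using a permutation test at a 2.5% significance level". Both endpoints must pass for the study to succeed, and SAP 21.0 concludes: "The familywise error rate is therefore controlled at 2.5% and no multiplicity adjustments are planned".

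SAP 24.0 sets the display precision: "The mean and standard deviation as well as any corresponding confidence intervals will be reported with one decimal place". Protocol 11.3 gives the expectation for Group B, that "tolerability scores are anticipated to be in the mild range".

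The readable text of SAP 11.2 names no bootstrap interval type, number of resamples or seed. Protocol 14.2, the protocol's Group B primary analysis section (14.4.2) and the opening of SAP 13.2 are blacked out, and only the heading of the code appendix (SAP 26.0) is readable.

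**The concern.** Two things look wrong.

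First, SAP 21.0 states error control at 2.5% without qualification. When both tests must pass, the worst-case study error equals the larger of the two test levels. The Group A permutation test holds its level under no effect, so the claim depends on Group B. A non-parametric bootstrap interval for a mean in 30 subjects is approximate, and most common types are somewhat too narrow at that size. If the true Group B mean were exactly 4.5 and Group A worked, the study could be declared successful more often than 2.5% of the time.

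Second, the printed precision equals the precision of the goal. Any bound from 4.45 to just under 4.55 prints as 4.5, so a reader of the report could not tell a pass from a fail in the one case where it matters.

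**Working it through.** **Inputs.** From the documents: n = 30 evaluable, two-sided 95% interval, limit 4.5, VAS 0-10, both tests required, Group A threshold p ≤ 0.025. Assumed: score distribution and SD, because the readable text gives neither.

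**1. Nominal level.** The upper limit of a two-sided 95% interval is a one-sided 2.5% test. This matches SAP 11.2 and 13.2.

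**2. Attained level, normal scores, percentile type.** The bootstrap standard error uses divisor n, so the level is

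P(t₂₉ < −1.96 × √(29/30)) = P(t₂₉ < −1.927) = 3.19%.

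The same formula gives 3.3% at n = 26 and 2.7% at n = 100.

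**3. Attained level by simulation** at a true mean of 4.5, n = 30. The main runs used 20,000 trials with 1,000 resamples each (Monte Carlo SE about 0.12 points). Ranges cover repeated runs and the SDs shown.

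| Assumed scores | Percentile | Basic | Normal-approx. | BCa | Studentized |
|---|---|---|---|---|---|
| Normal, SD 2 | 3.2-3.4% | 3.2-3.3% | 3.2% | 3.2-3.4% | 2.5-2.6% |
| Beta on 0-10, SD 1.5-3.5 | 3.2-3.6% | 3.6-4.0% | 3.4-3.6% | 2.4-3.3% | 1.6-2.6% |
| Right-skewed mixtures (skewness 0.6 and 1.4) | 4.0-6.1% | 5.5-7.8% | 4.6-6.7% | 2.6-4.5% | 1.3-3.8% |
| Left-skewed mixture (skewness −0.7) | 2.5% | 2.3% | 2.3% | 2.8% | 2.0% |

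The level can lie on either side of 2.5%, depending on the type and the shape. The documents fix neither in readable text.

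**4. Study-level error.** The groups are independent. With Group B at a true mean of 4.5, the percentile type, normal scores and Group A power of 0.95 to 1.00:

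0.95 × 3.19% = 3.03% to 1.00 × 3.19% = 3.19%.

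If neither group's null is false: 0.025 × 3.19% = 0.08%. The both-must-pass reasoning in SAP 21.0 is correct; it simply carries over whatever level Group B has.

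**5. The stated power.** The figure above 95% cannot be reproduced, because the assumed mean and SD are redacted. By the normal formula, SD ≤ (4.5 − μ) × √30 / (1.96 + 1.645). This allows SD up to 3.8, 3.0, 2.3 and 1.5 at true means of 2.0, 2.5, 3.0 and 3.5, so the claim is plausible for mild scores.

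**6. How often the bound prints as 4.5** (normal-approximation bound, beta scores):

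- mean 2.5, SD 2: 0.07% pass + 0.04% fail = 0.1%
- mean 2.5, SD 2.5: 0.48% + 0.41% = 0.9%
- mean 3.0, SD 2: 0.86% + 0.69% = 1.6%
- mean 3.0, SD 2.5: 1.92% + 1.71% = 3.6%, where power is only 88%

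Over all five interval types, the two cases with percentile power of 97 to 98% (mean 3.0, SD 2; mean 2.5, SD 2.5) give 0.8 to 2.8%. Rates of 7 to 11% arise only at means of 3.4 to 3.8, where power is roughly 50 to 77%, well below what SAP 13.2 states.

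**7. If the rounded bound were compared instead.** The effective limit becomes 4.45 and the percentile level falls to 2.4-2.7%. That reading is conservative.

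**8. What switching type would buy.** Power for percentile against studentized is 97.4% against 95.2% (mean 3.0, SD 2) and 98.0% against 95.5% (mean 2.5, SD 2.5). The tighter level costs 2.2 and 2.5 points of power.

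**The case for a change.** The best case for acting is that Group B is a single-arm comparison decided by one number, so a close result must be checkable. The normal-score calculation is not in dispute: four of the five common types run near 3.2% at n = 30, and right skew makes the percentile and basic types worse. The rounding point holds whatever interval type was chosen and owes nothing to redaction. Naming the type, comparing the unrounded bound, printing a second decimal and calling the level nominal would take a few sentences and cost no power.

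The arithmetic stands, and so does the observation that a printed 4.5 cannot be checked against the rule. The inference that the plan is wrong does not. Type, resample count and seed are what a code appendix usually holds, and that appendix is not readable here. If it specifies a studentized interval, the level is about 2.5% for normal scores and 1.6 to 2.6% for the beta shapes. The figure of 3.2% belongs to one assumed distribution. SAP 24.0 speaks only of how intervals are reported, and nothing readable tells the analyst to round before comparing. None of the suggested wording changes the test, the data analysed or the conclusion.

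**Conclusion.** No change to the plan is needed. The 2.5% level for Group B is a nominal level for an approximate method, stated in the usual way, and SAP 21.0 rightly needs no multiplicity adjustment. For normal scores and a non-studentized interval the worst-case study error is about 3.0 to 3.2%, an excess of 0.5 to 0.7 points. It arises only if the true Group B mean sits at 4.5 while Group A is effective. Under other shapes and types the Group B level ranged from 1.3% to 7.8%, so the documents do not establish that 2.5% is wrong. Moving to a studentized interval trades power for level and runs below 2.5% for most of the bounded shapes tried, so it is a sponsor's choice and not a correction.

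The decimal rule affects display only. If the bound fell between 4.45 and 4.55, an analyst would show enough digits to demonstrate whether the rule was met, and with scores in the mild range that situation is unlikely.

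These conclusions rest on assumed score shapes and SDs, on 30 evaluable subjects, and on reading SAP 11.2 as comparing the unrounded bound with 4.5.

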14.6. Handling Drop Outs or Missing Data

Group A Primary Endpoint: If a subject in Group A discontinues iontophoresis prior to the TM tap assessment or declines TM tap assessments, the subject will provide a VAS pain score for the attempted procedure and will be included in the analysis of the primary endpoint. [REDACTED]

[REDACTED]

[REDACTED] Reasons for discontinuation will be documented and presented in the clinical study report.

Group B Primary Endpoint: If a subject in Group B discontinues iontophoresis or tube placement, the subject will provide a VAS pain score for the attempted procedure. Subjects with discontinued procedures will be included in the sensitivity analyses only, and will not be included in the primary analysis. Only subjects with scores after tubes are successfully placed in all indicated ears (one tube if indicated for unilateral treatment and two tubes if indicated for bilateral treatment) will be included in the primary analysis. [REDACTED]

[REDACTED]

[REDACTED] Reasons for discontinuation will be documented and presented in the clinical study report.

[REDACTED]

[REDACTED]

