16.0 PREMATURE TERMINATION OR WITHDRAWAL

16.1. Subject Stopping Criteria

Subjects who do not complete the study procedure will be encouraged to remain in the study to complete post-procedure evaluations. If a subject withdraws prematurely from the study, a genuine effort must be made to determine the reason(s) why the subject failed to return for the procedure or follow-up visit or discontinued the study, and the reason must be recorded on the appropriate CRF.

Potential reasons for discontinuation include:

- Subject decides it is in their best interest to withdraw
- Subject expresses intolerable discomfort during the procedure and indicates they wish to stop the procedure and withdraw

- Serious adverse event that requires withdrawal from the study
- Investigator decides it is in the subject's best interest to be withdrawn if subject is experiencing intolerance or intolerable reaction to the procedure.

If the subject wishes to discontinue participation in the study, the Investigator will attempt to have the subject continue participation to complete follow-up assessments unless the subject's safety is compromised. All Serious Adverse Events that have not resolved by the end of the subject's participation in the study, must be followed until the event resolves, stabilizes or becomes non-serious.

All potential subjects in the study will be verbally informed and will sign an informed consent in compliance with 21CFR §50 that states that any withdrawal from the study will neither prejudice nor in any way affect their future treatment.

Prior to designating a subject as lost to follow-up, the site must provide documented evidence of three (3) good faith attempts to contact the subject to which there has been no response. At that point the subject will be considered lost-to-follow-up and withdrawn from the study.

■ [REDACTED]

[REDACTED]
[REDACTED]
[REDACTED]

- [REDACTED]
- [REDACTED]
- [REDACTED]
- [REDACTED]

[REDACTED]
[REDACTED]

- [REDACTED]
- [REDACTED]
[REDACTED]
[REDACTED]
- [REDACTED]
[REDACTED]
- [REDACTED]
[REDACTED]

[REDACTED]

[REDACTED]

[REDACTED]

[REDACTED]

[REDACTED]

[REDACTED]

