17.0 Handling of Missing Data

Missing data and the causes of the missing data will be summarized and presented. The number and proportion of subjects eligible for and compliant with all follow-up examinations will be presented. Subjects who withdraw from the study will be tabulated with the reasons for the withdrawal. Subjects who initiate the procedure, regardless of tolerability outcome or anesthesia effectiveness, will be encouraged to return for all follow-up assessments.

Group A Primary Endpoint: If a subject in Group A discontinues iontophoresis prior to the TM tap assessment or declines TM tap assessments, the subject will provide a VAS pain score for the attempted procedure and will be included in the analysis of the primary endpoint. [REDACTED]

[REDACTED]

[REDACTED] Reasons for discontinuation will be documented and presented in the clinical study report.

Group B Primary Endpoint: If a subject in Group B discontinues iontophoresis or tube placement, the subject will provide a VAS pain score for the attempted procedure. Subjects with discontinued procedures will be included in a sensitivity analysis, but will not be included in the primary analysis. Only subjects with VAS scores after tubes are successfully placed in all indicated ears (one tube placed if indicated for unilateral treatment and two tubes placed if indicated for bilateral treatment) will be included in the primary analysis. If a bilateral subject has successful tube placement for one ear, but the second ear is discontinued, the higher ('worst') VAS score will be used for the sensitivity analysis. [REDACTED]

[REDACTED] Reasons for discontinuation will be documented and presented in the clinical study report.

[REDACTED]

[REDACTED]

[REDACTED]

[REDACTED]

[REDACTED]

[REDACTED]

[REDACTED]

[REDACTED]

[REDACTED]

[REDACTED]

[REDACTED]

[REDACTED]

- [REDACTED]
- [REDACTED]
- [REDACTED]

[REDACTED]

- [REDACTED]
- [REDACTED]

[REDACTED]

[REDACTED]

[REDACTED]

[REDACTED]

[REDACTED]

[REDACTED]

[REDACTED]

[REDACTED]

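### The Group B success test uses completers only, so subjects who stop because of pain are left out although their VAS is collected, and SAP 11.2 names conflicting populations

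*SAP*

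**What the plan says.** SAP 11.2 describes the population for one test in three ways. It first refers to the mean score "for subjects in the Group B cohort, for whom tube placement was attempted, will be evaluated against a Performance Goal". It then states "The primary endpoint will be evaluated in the Per Protocol set using the bootstrap method at a 2.5% significance level". It ends with the completer rule: "Only completers, i.e., subjects with VAS scores after successful tube insertion in all indicated ears will be included in the primary analysis". Success is "demonstrated if the upper confidence bound of a 95% non-parametric bootstrap confidence interval on the mean score is below 4.5".

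The completer rule is the operative one. SAP 17.0 repeats it: "Subjects with discontinued procedures will be included in a sensitivity analysis, but will not be included in the primary analysis". So does Protocol 14.6: "Subjects with discontinued procedures will be included in the sensitivity analyses only, and will not be included in the primary analysis".

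The excluded subjects are not without data. Protocol 11.2, 11.5 and 14.6 and SAP 17.0 all have a subject who discontinues give a VAS for the attempted procedure. Protocol 16.1 lists among the reasons for discontinuing: "Subject expresses intolerable discomfort during the procedure and indicates they wish to stop the procedure and withdraw". SAP 17.0 also covers a mixed case, "If a bilateral subject has successful tube placement for one ear, but the second ear is discontinued"; the worse of that subject's scores goes to the sensitivity analysis only.

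SAP 7.2.1 defines a Full Analysis Set (FAS) of everyone in whom lidocaine solution is introduced into the ear canal.

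**The concern.** The endpoint is pain, and pain is a foreseen reason for not completing. Whether a subject counts can therefore depend on that subject's outcome. Group B has no control arm in which the same selection might cancel. If those who stop have more pain on average than completers, the completer mean understates the pain of those treated.

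The Per Protocol restriction opens a second way out, because SAP 7.2.2 treats abbreviated iontophoresis as a major deviation. The completer rule also drops a bilateral subject with one tube placed and the other ear stopped, although a true insertion score exists for the first ear.

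Group A does the opposite. Under Protocol 14.3.2.1 and SAP 7.1.1, subjects who discontinue or decline the tap stay in the primary mITT analysis with an attempted-procedure score. The objective in SAP 2.0 is tolerability, and both groups must pass for the study to succeed.

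The concern is limited to stops linked to pain. A subject with poor anesthesia whose tubes are all placed remains in the analysis.

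**Working it through.** **Inputs from the documents.** One-sided level 2.5%, 30 evaluable subjects and power above 95% (SAP 13.2); goal 4.5 and the success rule (SAP 11.2).

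**Inputs assumed.** The planning mean and SD are redacted, and no Group B stopping rate or score for those who stop is given. I take SD 2.5 (also 2.0 and 3.0), a stopping fraction p of 1/30, 5% or 10%, and a mean VAS among those who stop, m_d, of 6 to 8.

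**The plan's own figure.** Power above 95% cannot be reproduced without the planning values. Solving backwards with SD 2.5, the standard error is 2.5/√30 = 0.456, and the true mean must be at most 4.5 − (1.960 + 1.645) × 0.456 = 2.85. That fits the mild range anticipated in Protocol 11.3.

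**Effect of leaving out those who stop.** Let M be the mean over all treated subjects.

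- Completer mean: m_c = (M − p·m_d)/(1 − p)
- Chance of passing with 30 completers: Φ(−1.96 + (4.5 − m_c)/(SD/√30))

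Example with M = 4.5, p = 0.10, m_d = 8: m_c = (4.5 − 0.8)/0.9 = 4.111; (4.5 − 4.111)/0.456 = 0.852; Φ(−1.108) = 13.4%.

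False success, SD 2.5:

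| True all-treated mean M | m_d | No stopping | 1 in 30 | 5% | 10% |
|---|---|---|---|---|---|
| 4.5 | 4.5 | 2.5% | 2.5% | 2.5% | 2.5% |
| 4.5 | 6 | 2.5% | 3.2% | 3.7% | 5.5% |
| 4.5 | 7 | 2.5% | 3.8% | 4.7% | 8.8% |
| 4.5 | 8 | 2.5% | 4.5% | 6.0% | 13.4% |
| 4.75 | 8 | 0.6% | 1.2% | 1.7% | 4.3% |
| 5.0 | 8 | 0.1% | 0.2% | 0.3% | 1.0% |

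At M = 4.5 and m_d = 8, SD 2.0 gives 5.2%, 7.3% and 18.5%; SD 3.0 gives 4.1%, 5.2% and 10.6%.

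**Check with the bootstrap rule itself.** The simulation used 5,000 trials of 1,000 resamples, n = 30, beta-distributed VAS, completer SD 2.5 and SD 1.5 among those who stop. A trial passes if the 97.5th percentile of the bootstrap means is below 4.5. The simulation error is at most about 0.5 percentage points. At M = 4.5 and m_d = 8:

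| Analysis | 1 in 30 | 5% | 10% |
|---|---|---|---|
| Completers | 6.0% | 7.4% | 15.5% |
| FAS | 3.0% | 3.5% | 3.1% |

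With no stopping the bootstrap passes 3.1% of the time. That excess over 2.5% belongs to the bootstrap at this sample size and is not part of this point.

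**The case against.** The strongest reply is that the endpoint is pain following tube placement, collected after the manipulations needed to place the tube. A subject who stops during iontophoresis has no such score, and the attempted-procedure VAS measures something else. On that view the completer mean is a legitimate target, and against it the normal-formula level is still 2.5%. This stands as a point about the estimand: false success above is measured against the all-treated mean. It does not explain the attempted-placement wording in SAP 11.2, or why a bilateral subject with a true insertion score is dropped. It also sits badly with a tolerability objective.

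Second, the rule is prespecified, agrees across both documents, and is paired with a sensitivity analysis and reporting of reasons for stopping. That is true, but prespecification does not remove selection on the outcome. Some text after the discontinuation rules is redacted, so the claim covers only the visible rule.

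Third, the magnitude rests on assumed inputs and a true mean on the boundary. That is correct; the rates fall quickly above 4.5.

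Fourth, the rule drops all non-completers, including technical failures who may score low, and the FAS can err the other way. Suppose completers average 4.5 with SD 2.5 and technical stops average VAS 2 with SD 1. The FAS mean is then 4.417 with 1 in 30 stopping and 4.250 with 10%, and the FAS passes 3.8% and 7.9% of the time. This stands, and the fix needs a supportive analysis to expose it. Copying Group A, which excludes stops unrelated to discomfort, is a possible alternative. But Group B is an open single arm, and a subject with painful repeat attempts (Protocol 12.5.10) could be recorded as a technical stop.

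**Conclusion.** The concern holds and should be fixed before analysis. As written, the test that decides Group B, and with it the study, leaves out subjects who stop because of pain while holding their scores. SAP 11.2 also contradicts itself on who is analysed.

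The bias runs toward success when those who stop have more pain than completers. It is absent if nobody stops or if they average the same pain. The 3.2–4.5% and 5.5–13.4% ranges show a plausible scale under the stated assumptions; they do not estimate what this trial will see.

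**What to change.** In SAP 11.2 and 17.0 and Protocol 14.6:

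- Make the FAS, as already defined, the primary Group B set.
- Use the worst-ear VAS, and the attempted-procedure VAS for anyone who discontinues.
- Exclude no one on the recorded reason for stopping.
- Reword the population sentences in SAP 11.2 so that they all name this one set.
- Align the term evaluable in Protocol 11.4 and SAP 13.2, and recheck the power statement.

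Report three supportive analyses: completers/Per Protocol; subjects with placement attempted; and the FAS without stops recorded as unrelated to discomfort. The last shows whether low-scoring technical stops pull the mean down.

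**Cost.** No new data are needed. The mean may be less favourable, and some scores will rate an attempted procedure and not a tube insertion.

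Power may fall. Assume completers average 2.85 with SD 2.5 (95% power with 30), and those who stop have SD 1.5. The FAS mean is (1 − p)·2.85 + p·m_d, and its variance is (1 − p)·2.5² + p·1.5² + p(1 − p)(m_d − 2.85)². For p = 0.10 and m_d = 8 the mean is 3.365 and the SD 2.87, so power is Φ(−1.96 + 1.135/(2.87/√30)) = 58%. With 30 FAS subjects:

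| m_d | 1 in 30 | 5% | 10% |
|---|---|---|---|
| 6 | 92% | 89% | 80% |
| 8 | 87% | 80% | 58% |

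The sponsor should repeat this with the actual planning values.
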